5.2 SECONDARY ENDPOINT(S)

5.2.1 Key secondary endpoint(s)

Not applicable

5.2.2 Secondary endpoint(s)

The secondary endpoints are listed below.

- Change from baseline in Eczema Area and Severity Index (EASI) Score at Week 48

The actual and percent change from baseline as well as the absolute values at visits will be analysed.

The EASI total score assesses the extent of disease (area affected) at four body regions: head, trunk, upper limb, and lower limb for which the following scoring will be used:

% involvement	0	1 to <10%	10 to <30%	30 to <50%	50 to <70%	70 to <90%	90 to 100%
Region score	0	1	2	3	4	5	6

The severity of each of the four clinical signs: erythema, induration/papulation, excoriation, and lichenification using the following severity scale for each body region:

- 0 for “None”
- 0.5 for “None to Mild”
- 1 for “Mild”
- 1.5 for “Mild to Moderate”
- 2 for “Moderate”
- 2.5 for “Moderate to Severe”
- 3 for “Severe”

The following formula will be used to derive the EASI Total Score:

$$\begin{aligned}
 \text{EASI Total Score} = & (\text{Erythema}_{\text{Head}} + \text{Edema/papulation}_{\text{Head}} + \text{Excoriation}_{\text{Head}} + \\
 & \text{Lichenification}_{\text{Head}}) \times (\text{Head}_{\text{Region Score}}) \times 0.1 + \\
 & (\text{Erythema}_{\text{Trunk}} + \text{Edema/papulation}_{\text{Trunk}} + \text{Excoriation}_{\text{Trunk}} + \\
 & \text{Lichenification}_{\text{Trunk}}) \times (\text{Trunk}_{\text{Region Score}}) \times 0.3 + \\
 & (\text{Erythema}_{\text{Upper limb}} + \text{Edema/papulation}_{\text{Upper limb}} + \text{Excoriation}_{\text{Upper limb}} + \\
 & \text{Lichenification}_{\text{Upper limb}}) \times (\text{Upper_limb}_{\text{Region Score}}) \times 0.2 + \\
 & (\text{Erythema}_{\text{Lower limb}} + \text{Edema/papulation}_{\text{Lower limb}} + \text{Excoriation}_{\text{Lower limb}} + \\
 & \text{Lichenification}_{\text{Lower limb}}) \times (\text{Lower_limb}_{\text{Region Score}}) \times 0.4
 \end{aligned}$$

- 50% improvement from baseline in EASI (EASI50) at Week 48

Numbers and percentages will be analysed.

Achievement of Decrease in EASI ≥ xx% (EASIxx)

Achieving an improvement of xx% or larger decrease from baseline in EASI score is denoted as EASIxx. The EASIxx represents a binary variable with values of 0 (= non-response) or 1 (=response).

It is calculated based on the following approach (with xx taking a value of 50 or 75):

$$\text{If } \left\{ \frac{EASI(BL) - EASI(current)}{EASI(BL)} \times 100 \right\} \geq xx \text{ then EASIxx} = 1,$$

else EASIxx = 0.

- 75% improvement from baseline in EASI (EASI75) at Week 48

Numbers and percentages will be analysed.

- Change from baseline in SCORing of Atopic Dermatitis (SCORAD) at Week 48

The actual and percent change from baseline as well as the absolute values at visits will be analysed.

The SCORAD consists of three elements: extent of disease, intensity of disease, and subjective symptoms (Pruritus and Sleep Loss). It sums up to a maximum of 103 points. Two of the SCORAD items are subjective symptoms (C) assessed on Visual Analog Scales (VAS) from 0 to 10: Pruritus VAS and Sleep Loss VAS.

The following formula will be used to calculate the SCORAD element assessing the Extent of the disease:

$$\text{Extent Score}(A) = (\text{Face}_{\text{Front}} \times 4.5 + \text{Upper_Limbs}_{\text{Front}} \times 9 + \text{Trunk}_{\text{Front}} \times 18 + \text{Lower_limbs}_{\text{Front}} \times 18 + \text{Genitals}_{\text{Front}} \times 1 + \text{Head}_{\text{Back}} \times 4.5 + \text{Upper_limbs}_{\text{Back}} \times 9 + \text{Trunk}_{\text{Back}} \times 18 + \text{Lower_limbs}_{\text{Back}} \times 18) / 100$$

In the SCORAD element assessing the Intensity of the disease the following scoring will be used:

- 0 for “Absence”
- 1 for “Mild”
- 2 for “Moderate”
- 3 for ”Severe”

The SCORAD Intensity score element will be derived using the formula below:

$$\text{Intensity Score}(B) = (\text{Erythema_Score} + \text{Edema/Papulation_Score} + \text{Oozing/crusts_Score} + \text{Excoriations_Score} + \text{Lichenification_Score} + \text{Dryness_Score})$$

For the SCORAD element subjective symptoms the following formula will be used:

$$\text{Subjective symptoms}(C) = \text{Pruritus_VAS} + \text{Sleep_Loss_VAS}$$

The following formula will be used to calculate the SCORAD Total Score:

$$\text{SCORAD Total Score} = (A/5) + (B \times 7/2) + C$$

- Patients achieving at least a 2-grade reduction from baseline to clear (0) or almost clear (1) in the Investigator's Global Assessment (IGA) at Week 48

Numbers and percentages will be analysed.

IGA score allows investigators to assess the overall disease severity at one given time point. It is a 5-point scale with: 0 = clear, 1 = almost clear, 2 = mild, 3 = moderate, and 4 = severe. The overall IGA score includes the assessment of erythema, induration/papulation, lichenification, and oozing/crusting. For the first three sections the following scale will be used:

- "None"
- "Barely Perceptible" ("Minimal" for lichenification)
- "Slight but Definite"
- "Clearly Perceptible"
- "Marked"

[figure not shown]
For oozing/crusting the available answers are "None" or "Present."

[figure not shown]
The following instructions will be used to derive the **IGA Score**:

- IGA Score = 0 if the answers in all sections are "None".
 - IGA Score = 1 if any of the following occurred: (erythema is barely perceptible OR induration/papulation is barely perceptible OR lichenification is minimal) AND no oozing/crusting is observed.
 - IGA Score = 2 if any of the following occurred: (erythema is slight but definite (pink) OR induration/papulation is slight but definite OR lichenification is slight but definite), AND no oozing/crusting is observed.
 - IGA Score = 3 if any of the following occurred: erythema is clearly perceptible (dull red) OR induration/papulation is clearly perceptible OR lichenification is clearly perceptible OR oozing/crusting is present.
 - IGA Score = 4 if any of the following occurred: erythema is marked (deep or bright red) OR induration/papulation is marked OR lichenification is marked.
- Note: For IGA score of 4, the oozing/crusting may be present.

5.4.1 Safety

Safety will be assessed based on:

6. GENERAL ANALYSIS DEFINITIONS

6.1 TREATMENT(S)

For basic study information on the treatment to be administered, assignment to treatment, and selection of dose, cf. Section 4 of the CTP.

All patients will receive subcutaneous doses of 600 mg of BI 655130 solution for SC injection (every four weeks).

The following trial phases are defined:

Table 6.1: 1 Flow chart of trial phases

Trial phase	Description	Start (included)	End (excluded)
Open label Treatment phase	On-treatment period	Date of start of injection of first study drug (Day 1)	EoT visit date + 1 day
Follow-up phase	Off-treatment follow-up period	EoT visit date + 1 day	Date of EoS Participation visit + 1 day

Dates are defined individually per patient. If more than one date is associated with a specific visit, measurements associated with a specific date are assigned to a study analysis phase according to the rules specified in the table. An analysis phase will not extend beyond the start date of the following phase.

EoT = End of treatment; EoS = End of study;

Patients who discontinue the treatment but will continue on trial visits will be included in analyses with the available data. For patients who discontinue the trial prematurely only available data will be used in the analyses.

The time windows for data presentation in the analysis are described in [Table 6.7: 1](#).

Treatment group will be labelled as follows: "**Speso 600 mg SC q4w**" (i.e., patients receiving BI 655130 600 mg). In addition, the descriptive statistics will be presented for the following groups:

- By treatment received in the parent trial (1368-0032):
 - "Placebo" followed by "Speso 600 mg SC q4w"** – patients who were randomised to receive placebo in the double-blind period of the parent trial and received Speso treatment in the open-label period of the parent trial
 - "Placebo" followed by "no Speso 600 mg SC q4w"** – patients who were randomised to receive placebo in the double-blind period of the parent trial and

didn't receive Speso treatment in the open-label period of the parent trial (but didn't discontinue the parent study prematurely)

- **"Speso 600 mg SC q4w" followed by "Speso 600 mg SC q4w"** – patients who were randomised to receive active treatment (Speso) in the double-blind period of the parent trial and received Speso treatment in the open-label period of the parent trial
- **"Speso 600 mg SC q4w" followed by "no Speso 600 mg SC q4w"** – patients who were randomised to receive active treatment (Speso) in the double-blind period of the parent trial and didn't receive Speso treatment in the open-label period of the parent trial (but didn't discontinue the parent study prematurely)
- **"Overall Total"** – all patients from FAS, regardless of the treatment received in the parent trial.

2. By the response achieved at Week 16 of the parent trial (1368-0032):

- **"Responders"** – patients who attained at least 75% reduction in EASI score at Week 16 compared to baseline during the parent trial
- **"Non-responders"** – patients who attained less than 75% reduction in EASI score at Week 16 compared to baseline during the parent trial
- **"Overall Total"** – all patients from FAS, regardless of the EASI response status at Week 16 in the parent trial.

More details on the technical implementation of these analyses are provided in the ADS Plan of this TSAP.

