7.2.5 Safety analyses

Adverse events will be coded using the Medical Dictionary for Drug Regulatory Activities (MedDRA). Standard BI summary tables and listings will be produced. All adverse events with an onset between start of treatment and end of the REP, a period of 16 weeks after the last dose of trial medication, will be assigned to the on-treatment period for evaluation.

All treated patients will be included in the safety analysis. In general, safety analyses will be descriptive in nature and will be based on BI standards. No hypothesis testing is planned.

Statistical analysis and reporting of adverse events will concentrate on treatment-emergent adverse events, i.e. all adverse events occurring between start of treatment and end of the REP. Adverse events that start before first drug intake and deteriorate under treatment will also be considered as 'treatment-emergent'.

Frequency, severity, and causal relationship of adverse events will be tabulated by system organ class and preferred term after coding according to the Medical Dictionary for Drug Regulatory Activities (MedDRA).

Laboratory data will be analysed both quantitatively as well as qualitatively. The latter will be done via comparison of laboratory data to their reference ranges. Values outside the reference range as well as values defined as clinically relevant will be summarised. Groups (defined in [Section 7.2.1](#)) will be compared descriptively with regard to distribution parameters as well as with regard to frequency and percentage of patients with abnormal values or clinically relevant abnormal values.

Vital signs, physical examinations, or other safety-relevant data observed at baseline, during the course of the trial and at the end-of-trial evaluation will be assessed with regard to possible changes compared to findings before start of treatment.

[REDACTED]

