6.7 BASELINE, TIME WINDOWS AND CALCULATED VISITS

Measurements reported with date and time and taken prior to start of administration of trial treatment will be considered pre-treatment values. Measurements reported with a date only (and no time) and taken on the day of first administration of trial treatment will also be considered pre-treatment values. These pre-treatment values will be assigned to visits according to the nominal visit number as recorded on the eCRF or as provided by the laboratory. For definitions used in Safety analyses, refer to [Section 7.8](#).

There will be two different baseline definitions used in the analyses:

1. Baseline for this extension trial – defined as the last measurement recorded before the first trial medication administration in this study.

2. Baseline for the parent trial (1638-0032) – defined as the measurement recorded at randomisation visit (Visit 2) of the parent trial. If the data at Visit 2 is missing, then the data from Visit 1 of the parent trial will be considered baseline.

Two separate analyses will be conducted, using the baselines as defined above.

Measurements taken after start of administration of trial treatment will be considered either on- or off-treatment values based on the definition in [Section 6.1](#), and will be assigned to visits for statistical analysis, if applicable, as defined below.

Analysis of AE data, concomitant medication or non-drug therapies will not be based on visits. Therefore, no assignment to time windows will be necessary for such data.

For derivation of the last value on treatment, minimum value on treatment, and maximum value in the trial phase, all values from the relevant phase (whether or not collected in any time window; see [Table 6.1: 1](#) for definition of the trial phases) will be considered; these will be derived for analysis of laboratory and vital signs data. For identification of potentially clinically significant abnormal laboratory values, all values (whether or not selected in any time window) before the date of EoS Participation visit will be considered.

A graphical analysis of the ALT and total bilirubin will be performed (so called eDISH plot) based on the available data obtained during the on-treatment period.

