7.8.1 Adverse Events

AEs will be coded with the most recent version of MedDRA.

The analyses of AEs will be descriptive in nature. All analyses of AEs will be based on the number of patients with AEs and not on the number of AEs. System organ classes (if applicable) will be sorted according to the standard sort order specified by the EMA, preferred terms (if applicable) will be sorted by total frequency (within system organ class) across all treatment arms.

For further details on summarization of AE data, please refer to “Analysis and Presentation of Adverse Event Data from Clinical Trials” [BI-KMED-BDS-HTG-0066] (4) and “Handling of missing and incomplete AE dates” [BI-KMED-BDS-HTG-0035] (3).

The analysis of AEs will be based on the concept of treatment emergent AEs. If only the start date of an AE is collected (without start time), any AE occurrence on the same day as the first BI 655130 administration will be assigned to the on-treatment phase.

An overall summary of AEs will be presented by treatment.

This overall summary will include summary statistics for the class of other significant AEs (sponsor definition based on ICH E3 (6)) and for the class of AESIs.

The following are considered an AESI in this trial:

- Hepatic injury
- Systemic hypersensitivity reactions including anaphylactic reaction
- Severe infections (according to RCTC grading in the ISF)
- Opportunistic and mycobacterium tuberculosis infections

The investigator has to classify on the eCRF whether an observed AE was an AESI or not. Only those AEs that are indicated by the investigator as AESI in the eCRF will be analysed in this category.

Based on the specification provided in ICH E3 (6), the sponsor has defined AEs which are to be classified as ‘other significant’. These will include those non-serious AEs which were reported with ‘action taken = Drug withdrawn’ or ‘action taken = Dose reduced’.

The frequency of patients with AEs will be summarised by treatment, primary system organ class and preferred term. AEs which were considered by the investigator to be drug related will be summarised separately (secondary safety endpoint of this trial). Separate tables will also be provided for patients with SAEs, patients with drug-related SAEs, patients with AESIs, patients with AE leading to discontinuation of the trial, and patients with other significant AEs (as described previously). AEs will also be summarized by maximum RCTC grade.

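### The visible SAP sets no end date for treatment-emergent AEs, and its only on-treatment period stops at EoT while the protocol's runs to 16 weeks after the last dose

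*SAP*

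**What the plan says.** **Protocol 7.2.5 (Safety analyses).** The on-treatment period for AEs takes in "All adverse events with an onset between start of treatment and end of the REP, a period of 16 weeks after the last dose". The same span defines a treatment-emergent AE. The section adds a second route into that class: "Adverse events that start before first drug intake and deteriorate under treatment will also be considered". Protocol 1.2.1.1 gives the REP as 16 weeks.

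**SAP 6.1, Table 6.1:1.** The on-treatment period starts at the first injection. Its end, as an excluded bound, is "EoT visit date + 1 day", so its last day is the EoT visit. The time from there to EoS is named an off-treatment follow-up period, and a phase may not run past the start of the next one.

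**SAP 6.7.** Its rule for measurements points to Section 6.1: "Measurements taken after start of administration of trial treatment will be considered either on- or off-treatment values based on the definition in". The same section says "Analysis of AE data, concomitant medication or non-drug therapies will not be based on visits". Its paragraph on pre-treatment values closes with a pointer to Section 7.8: "For definitions used in Safety analyses, refer to".

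**SAP 7.8.1 (Adverse Events).** "The analysis of AEs will be based on the concept of treatment emergent AEs". The only boundary rule concerns the first day: where no start time is collected, "any AE occurrence on the same day as the first BI 655130 administration will be assigned to the on-treatment phase". No end is stated, and neither the REP nor 16 weeks is mentioned.

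**SAP 3.** The plan says that it rests on the analysis specification in protocol Section 7.

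**The concern.** One term has two end dates, and the SAP's AE section uses that term without saying which date it means. A programmer working from the visible SAP finds a single definition of an on-treatment period, and it ends at EoT. The protocol ends its AE period 16 weeks after the last dose.

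At stake are AEs with onset after EoT but inside the REP. The protocol describes this as time when drug levels or pharmacodynamic effects are still likely to be present. Under Table 6.1:1 these events would leave the treatment-emergent summaries: the overall AE table and the SAE and AESI tables. They would still be collected, and they would still be listed, because SAP 7 lists individual values from the off-treatment period too. In a long-term safety trial of about 40 patients, the summary tables are the main output.

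**Working it through.** **Inputs from the documents**
- REP: 16 weeks = 16 × 7 = 112 days (Protocol 1.2.1.1, 7.2.5).
- Planned EoT is Day 1429 and planned EoS is Day 1541 (Flow Chart; SAP Table 6.7:1).
- Completers receive their last dose at EoT. Early stoppers receive no dose at EoT and attend it as soon as possible (Flow Chart footnotes 15 and 4).
- Week 48 is planned Day 337, which is 336 days after Day 1.

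**Assumptions**
- The gap from last dose to EoT in early stoppers is not fixed by the documents. I use 7, 28, 56 and 112 days. It exceeds zero because no dose is given at that visit. A gap of about 112 days arises under Protocol 3.3.4.1 for a patient stopped after missing more than 3 consecutive doses: the fourth missed 4-weekly visit falls 4 × 28 = 112 days after the last dose.
- The Week 48 count is cut at planned Day 337.

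**Check of the plan's own figure.** 1429 + 112 = 1541, which matches the planned EoS day.

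**Completers.** The protocol window runs from Day 1 to Day 1541, or 1540 elapsed days. Table 6.1:1 stops at Day 1429. The loss is 1541 − 1429 = 112 days, and 112/1540 = 7.3%. Nothing is lost at Week 48, because EoT is far beyond Day 337.

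**Early stoppers, whole trial.** Loss = max(112 − gap, 0), which gives 105 / 84 / 56 / 0 days for gaps of 7 / 28 / 56 / 112 days.

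**Early stoppers, Week 48 count.** With w the week of the last dose:
- protocol days = min(7w + 112, 336)
- Table 6.1:1 days = min(7w + gap, 336)
- loss = the difference

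| Last dose | Protocol days | Gap 7 | Gap 28 | Gap 56 | Gap 112 |
|---|---|---|---|---|---|
| Week 12 | 84 + 112 = 196 | 105 (54%) | 84 (43%) | 56 (29%) | 0 |
| Week 24 | 168 + 112 = 280 | 105 (38%) | 84 (30%) | 56 (20%) | 0 |
| Week 36 | min(364, 336) = 336 | 77 (23%) | 56 (17%) | 28 (8%) | 0 |
| Week 44 | min(420, 336) = 336 | 21 (6%) | 0 | 0 | 0 |

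Example, Week 44 with a 7-day gap: 336 − (308 + 7) = 21. The zero at 28 days arises only because 308 + 28 = 336.

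The percentages are shares of one patient's observation time, not of patients or events. No patient count can be derived, because the documents give neither the number of early stoppers nor an AE rate.

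**The case against.** The strongest reply is that there is no rival definition of a treatment-emergent AE. Protocol 7.2.5 is the only one in either document, SAP 7.8.1 uses the term without redefining it, and SAP 3 tells the reader to work from protocol Section 7. Where the SAP wants the EoT-based phase, it points to it: SAP 6.7 for measurements, 7.2 for concomitant medication, 7.8.3 for vital signs. The AE section has no such pointer. The reference in SAP 6.7 to Section 7.8 closes a paragraph on pre-treatment values, so it is weak evidence that 7.8 was meant to hold an AE end date. The body of SAP 5.4.1 is not visible, and neither the analysis dataset plan nor the internal AE guidance is available here. Any of them may state the window.

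Most of this stands. It rules out a stronger reading that a reader might infer: that the SAP discards REP events or replaces the protocol's definition. The documents do not show that, because Table 6.1:1 is never expressly applied to AEs.

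The reply does not settle the text, however. SAP 7.8.1 does speak of an on-treatment phase, and Table 6.1:1 holds the only visible definition of one. That AE analysis is not based on visits does not remove AEs from the table's reach: SAP 6.7 groups concomitant medication with AEs on that point, yet SAP 7.2 still ties concomitant medication to Section 6.1. Where the SAP wants data beyond EoT it can say so, as it does for clinically significant laboratory values up to EoS.

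**Conclusion.** The point holds as an unresolved conflict between two end dates for one term, with the protocol window as the likely intent. It matters only if the EoT-based phase is applied to AEs. The main exposure is then the whole-trial AE, SAE and AESI tables: 112 of 1540 days (7%) per completer, and 105 to 0 days per early stopper over assumed gaps of 7 to 112 days. A gap shorter than 7 days would lose slightly more.

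A reader might infer that the Week 48 primary endpoint is compromised. That is not supported. Any patient whose EoT falls on or after Day 337 is unaffected. The endpoint counts patients, so an early stopper's status changes only if the first treatment-emergent AE falls in the lost interval. The effect is small and can be nil. The opposite inference, that stopping as late as Week 44 can never matter, is also unsupported: it needs a gap of at least 28 days, and a visit due as soon as possible may come sooner.

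**What to change.** In SAP 7.8.1 (or 6.1), state that treatment-emergent AEs are those with onset from first dose to last dose date + 112 days (the REP), as defined in Protocol 7.2.5. Give this AE period a label distinct from the on-treatment period of Table 6.1:1, and keep that table for the other data. The reference to Protocol 7.2.5 also carries over its rule on events that begin before first intake and worsen under treatment, which an onset rule alone would leave out.

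The cost is one sentence in a SAP amendment and one extra derivation. No new data are needed, because Protocol 5.2.6.2.1 already collects all AEs to the patient's end of trial. The downside is two differently bounded periods in one report, which is why the labels must differ, and slightly higher AE counts than Table 6.1:1 would give.
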